Placement of spinal anesthesia- This will be performed by the attending anesthesiologist or anesthesiology resident who are providing anesthesia for the patient in the operating room. The anesthesia technique will be standardized. A spinal anesthetic will be performed in the sitting position at the lumbar vertebra level (L) either at L3-L4 or L4-L5 level. All women will receive a spinal anesthetic using 0.75% hyperbaric bupivacaine 912 mg plus fentanyl 20 micrograms plus epinephrine 1:100,000 100 micrograms administered intrathecally. The anesthesiologist caring for the patient will not be blinded. The anesthesiologist caring for the patient will open an opaque envelope handed to him/her by the research personnel. The envelope will clearly state the group the patient is assigned to and if ITM 200 micrograms should be added or excluded from the spinal medication. Spinal block efficacy will be considered successful if a sensory block to pinprick is achieved at a level of thoracic (T) 6 or higher. Anesthesia and surgery will be performed in the usual manner.

Placement of QL blocks- Immediately after wound closure, bilateral QL blocks will be placed by one of the investigators under direct ultrasound guidance (Sonosite X-Porte, Sonosite, Bothell, WA). For the purpose of our study we will be utilizing the QL 2 technique by Blanco to achieve blockade from T7-L1 dermatomes.(Blanco et al. 2016; Blanco, Ansari, and Grgis 2015) The anesthesiologist caring for the patient will open the opaque envelope and prepare the study drug. The study drug will either be a sham 20 ml empty syringe or 0.25% bupivacaine hydrochloride 20 ml each side. The patients will be in the supine position with a small roll of blanket placed under the ipsilateral flank. The abdomen will be cleaned with 2 % chlorhexidine gluconate and 70 % isopropyl alcohol solution (ChloraPrep® One-Step). If the patient has an allergy to any of the contents of

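### Intrathecal epinephrine is labelled with a concentration and a mass that agree only at 10 mL, and no volume is stated

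*Combined protocol and SAP*

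**What the plan says.** The spinal mixture is specified once, in section XVI (Study design), in the paragraph on placement of spinal anesthesia. The base is given as "All women will receive a spinal anesthetic using 0.75% hyperbaric bupivacaine 912 mg", followed by the additives: "plus fentanyl 20 micrograms plus epinephrine 1:100,000 100 micrograms administered intrathecally". The printed bupivacaine mass is probably a range whose dash was lost in text extraction. It is read here as 9-12 mg, as an assumption, and is not counted against the plan.

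The same paragraph states that "The anesthesia technique will be standardized". It lets either an attending or a resident perform the spinal. The only planned difference between arms is stated in the envelope instruction, which tells the anesthesiologist "if ITM 200 micrograms should be added or excluded from the spinal medication".

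No volume is given for the epinephrine or for the whole injectate, and the text does not say whether the ratio describes the source solution or the final mixture. The study drug list in section XIV does not include epinephrine, and no other section restates its dose.

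**The concern.** A ratio strength and a mass together fix a volume. Here that volume is several times the bupivacaine volume implied by the same sentence, and nothing mentions a dilution step or a total volume. Someone preparing the syringe has to decide what the ratio refers to, and different decisions lead to different injectates.

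The mixture goes intrathecally to every one of the 75 planned patients, prepared by whichever anesthesiologist is in the room. At stake are the safety of drug preparation and the uniformity of the spinal. The plan ties the spinal to trial conduct in two places. Success is a pinprick block at T6 or higher (section XVI), and failure of the spinal ends a patient's enrollment (section XVII, item 6). Section XIX allows for only 25 - 23 = 2 losses per group.

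**Working it through.** The plan states no volume, so it has no figure of its own to reproduce. The check is unit arithmetic on the figures in section XVI.

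**Inputs**
- Epinephrine: ratio 1:100,000 and mass 100 micrograms (section XVI).
- Bupivacaine: 0.75%, which is 7.5 mg/mL (section XVI). Mass taken as 9-12 mg (assumption, see above).
- Volumes of fentanyl and morphine: not stated, and left out unless noted.

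**Step 1: the volume at which ratio and mass agree**
- 1:100,000 = 1 g per 100,000 mL = 1,000,000 micrograms / 100,000 mL = 10 micrograms/mL.
- Volume = mass / concentration = 100 / 10 = 10 mL.

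**Step 2: bupivacaine volume**
- 9 / 7.5 = 1.2 mL; 12 / 7.5 = 1.6 mL.
- Ratio of the two volumes: 10 / 1.6 = 6.3 to 10 / 1.2 = 8.3.

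**Step 3: what each reading implies**
- *The ratio is the source solution and the mass holds.* 10 mL is added to the bupivacaine. Its concentration becomes 9 / (1.2 + 10) = 0.80 mg/mL, or 0.080%, up to 12 / (1.6 + 10) = 1.03 mg/mL, or 0.103%. Any further component would dilute it more.
- *The ratio is the final concentration and the mass holds.* The whole injectate is 10 mL. Bupivacaine is then 9 / 10 = 0.9 mg/mL, or 0.09%, up to 12 / 10 = 1.2 mg/mL, or 0.12%.
- *The ratio is the concentration in the bupivacaine volume.* Epinephrine is 10 x 1.2 = 12 micrograms up to 10 x 1.6 = 16 micrograms. The stated mass is 100 / 16 = 6.3 to 100 / 12 = 8.3 times as large.
- *The mass holds in the bupivacaine volume.* 100 / 1.2 = 83.3 micrograms/mL, which is 1:12,000; 100 / 1.6 = 62.5 micrograms/mL, which is 1:16,000. Neither is the printed ratio.

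**Step 4: sensitivity to the unstated total volume**
- If the other components brought the total to an assumed 1.5-3 mL, 1:100,000 as the final concentration would give 10 x 1.5 = 15 to 10 x 3 = 30 micrograms. The stated mass would be 100 / 30 = 3.3 to 100 / 15 = 6.7 times as large. The gap narrows but does not close.

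**The case against.** The strongest reply is that nothing here is a contradiction in the strict sense. A mass and a concentration can conflict only when a volume is also given, and none is. The mass is printed plainly as 100 micrograms, and no competing epinephrine dose appears anywhere. Fentanyl and morphine are also given by mass without a volume. This largely stands: the incompatibility is by implication, and the documents do not say what intrathecal volume is acceptable. It does not dispose of the point. Fentanyl and morphine carry no concentration label, so nothing has to be squared with their mass. The epinephrine does carry one, and it fits the mass only at a volume that sits poorly with the bupivacaine beside it.

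Four stronger readings are tempting, and the documents do not support them.
- A reader might infer that the epinephrine dose is undefined. The mass is stated; what is undefined is the volume and the meaning of the ratio. A different dose follows only if the ratio is allowed to override the printed micrograms.
- A reader might infer a 10- to 100-fold shortfall by supposing that 0.1-1 mL of the labelled solution is drawn up (1-10 micrograms). No such volume appears in the documents.
- A reader might take the printed bupivacaine mass literally, which would be 912 / 7.5 = 121.6 mL. A dash lost in extraction is the likelier explanation, so this is not counted as an error.
- A reader might infer bias or lost power. The mixture is common to all three arms, the primary outcome in section XII leaves out narcotic given in the spinal, and no calculation in section XIX uses the epinephrine. The preparer does know the allocation, so ad hoc choices could in principle differ by arm, but nothing in the plan shows that they would. Nor do the documents quantify any effect of the label on block height, spinal failure or early pain.

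**Conclusion.** The point holds as a specific mismatch, by implication, in the plan's figures for one component of the spinal. The unit conversion rests on no assumption: ratio and mass agree only at 10 mL. The size of the discrepancy does rest on assumptions. With bupivacaine at 9-12 mg, one reading dilutes it to about 0.08-0.10%, and another puts epinephrine at 12-16 micrograms, roughly 6- to 8-fold below the stated mass. Two providers could prepare different injectates and both claim to have followed the protocol, which undercuts the promise of a standardized technique.

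This matters for safety and standardization in all three arms alike. It does not by itself bias the between-group comparison. It goes beyond a clerical remark because the mixture is given intrathecally to every participant. No view is taken on which concentration, mass or volume is right.

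**What to change.** In the spinal anesthesia paragraph of section XVI, the investigators should reconcile the epinephrine ratio with the mass, using the preparation actually used. They should say whether the ratio refers to the source solution or the final mixture, and state the epinephrine volume and the total intrathecal volume. The bupivacaine mass can be checked against the source file at the same time, to confirm that the dash is present. Which figures are correct is for the investigators to decide.

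The cost is a one-line protocol correction and, if one is used, a matching drug-preparation sheet. No patients, procedures or analyses are added.

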Placement of QL catheters- A 20 G peripheral nerve polyamide catheter (Contiplex® Ultra 360™ continuous nerve block set, B Braun, Bethlehem, PA, USA) will be inserted through the 18 G echogenic needle under direct ultrasound visualization. The catheter will be secured using the standard technique employed at our institution. Correct placement of QL catheters will be confirmed by injecting saline under ultrasound guidance. QL catheter will be placed on both sides in a similar fashion. A member of the research team who performed the initial QLB in the operating room will attach a peripheral nerve pump (CADD® Solis ambulatory infusion pump, Minneapolis, MN, USA) to the QL catheter once the patient reaches the post anesthesia care unit (PACU). No infusion will be initiated if the patient is assigned to group 1 (Spinal anesthesia with ITM + US guided QLB single shot sham block + QLB catheters with no continuous infusion) and group 2 (Spinal anesthesia without ITM + US guided QLB single shot with bupivacaine hydrochloride + QLB catheters with no continuous infusion). Infusion of 0.2 % ropivacaine at 10 ml/hour on each side will be initiated if the patient is randomized to group 3 (Spinal anesthesia without ITM + US guided QLB single shot with bupivacaine hydrochloride + QLB catheters infusing 0.2% ropivacaine hydrochloride). A member of our research team who is blinded to the group allocation will manage all peripheral nerve catheters. No extra bolus medication will be given through any of the catheters. We are not initiating any infusion through the peripheral nerve catheters in group 1 and 2 to avoid the possibility of pain due to stretching of muscles and facial planes by normal saline.

All patients will be started on a multimodal pain regimen. They will receive scheduled acetaminophen 1000 mg orally and ibuprofen 600 mg every 6 hours. Oxycodone 2.5 mg-5 mg oral every 4 hours as needed will be added for breakthrough pain. Patients will be

evaluated by the anesthesia pain service for adding a PCA with intravenous hydromorphone if pain not adequately controlled on their regimen.

Our research personnel who will be blinded, will follow up patients for the first 48 hours to collect data listed under primary and secondary objectives. We are not assessing dermatomal levels to determine the spread of local anesthetic as it could possibly result in patients and study personnel knowing which group they fall under and potentially unblinding the study.

XVII. Conduct

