
1. Screening

Our research team will assess patients for eligibility based on the inclusion criteria. We will obtain informed written consent from all eligible patients. Any member of our research team at any point will obtain this consent during the preoperative period (anesthesia clinic, surgery clinic, preoperative holding area). Patients will be given adequate time to consult with family members and use the internet for additional information. All questions and concerns by the patient will be addressed at this point.

Once a written informed consent is obtained the patient will be educated about the study protocol, NPS assessment, other assessment tools and the use of MMP medications. Baseline pain score will be recorded at this point. A complete preoperative evaluation, physical examination and preoperative testing will be conducted per usual protocol by the anesthesiologist caring for the patient.

Three copies will be made of the written informed consent. Patient will be given a copy of the signed written informed consent. A copy of the consent will be placed in the patient's chart. Our research team will keep one copy of the consent.

2. Enrollment

Patient will be enrolled if all inclusion, exclusion criteria are met and the patient has provided an informed written consent. Our research coordinator will then randomly assign the patient into one of the groups based on the random allocation software.

3. Randomization and allocation concealment

Anesthesiologist in the operating room will not be blinded to the patient's randomization, as they must prepare the spinal with or without intrathecal morphine and the prescribed solution for block placement. Anesthesiologist performing the regional nerve block not be blinded as they will have to perform a

sham QLB or a QLB with the study drug. All other research personnel collecting data or seeing the patient postoperatively will not know what the contents of the spinal medication were, whether or not the QLB contained no drug or bupivacaine, or whether the QLB catheter infusions contain no drug or ropivacaine.

Patient's assigned group will be communicated to the anesthesiologist caring for the patient in an opaque envelope so that no other research personnel are wise to the assignment.

Research personnel responsible for randomizing and assigning group will not be the same personnel as those evaluating the patient or collecting data.

4. Preoperative assessment

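### One envelope tells the operating-room anesthesiologist group 2 versus group 3 before the spinal, although that split is needed only when the infusion is or is not started in the PACU

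*Combined protocol and SAP*

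**What the plan says.** Section XVI, Placement of spinal anesthesia, makes two statements about the person giving the anesthetic: "The anesthesiologist caring for the patient will not be blinded" and "The anesthesiologist caring for the patient will open an opaque envelope handed to him/her by the research personnel". On the contents it says: "The envelope will clearly state the group the patient is assigned to and if ITM 200 micrograms should be added or excluded". The opening must come before the spinal, because the ITM instruction is carried out there.

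At the block step (Placement of QL blocks) the same person acts again: "The anesthesiologist caring for the patient will open the opaque envelope and prepare the study drug". No second or staged envelope is described. The block itself is a different role: "bilateral QL blocks will be placed by one of the investigators under direct ultrasound guidance".

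For the PACU, Placement of QL catheters says: "A member of the research team who performed the initial QLB in the operating room will attach a peripheral nerve pump". Ropivacaine is then started in group 3 and nothing is started in groups 1 and 2.

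Section XVII.3 leaves the block operator unblinded: "Anesthesiologist performing the regional nerve block not be blinded as they will have to perform a" sham or an active block. The same section says that the assignment goes to the anesthesiologist in an opaque envelope so that nobody else on the research team learns it.

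**The concern.** Hypothesis 2 includes the comparison of the continuous catheter (group 3) with the single-shot block (group 2), and section XIX sizes that contrast. Up to the PACU the two arms should be indistinguishable to everyone giving care. Under the plan, at least one person giving care can tell them apart from before the spinal.

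Two things are at stake. Care before the PACU could differ between the arms. So could the set of patients who stay in the trial, because exclusion 11 (local anesthetic in another fascial plane) and exclusion 12 (sedation or general anesthesia during the cesarean) depend on events in the operating room, after the group is known. Sedation is largely the anesthesiologist's decision. The example given for exclusion 11 is infiltration by the surgeon, so that route is less direct.

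**Working it through.** No stated figure depends on this point, so the check is to set what each step requires beside what is disclosed.

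| Step | Group 1 | Group 2 | Group 3 | Needed at this step | Disclosed |
|---|---|---|---|---|---|
| Spinal | ITM | no ITM | no ITM | 1 versus 2/3 | full group |
| Block at wound closure | sham | bupivacaine | bupivacaine | 1 versus 2/3 | full group |
| Catheters, both sides | placed | placed | placed | nothing | full group already known |
| Pump in PACU | no infusion | no infusion | ropivacaine | 2 versus 3 | full group already known |

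The last column is for the operating-room anesthesiologist. The group definitions and the placement subsections of XVI supply the other entries.

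1. **Unavoidable disclosure.** Group 1 status must be known at the spinal and at the block. It also reveals that a group 1 catheter will not be infused. No envelope scheme can hide that.

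2. **Avoidable disclosure.** The group 2 versus 3 split does not alter any step before the PACU. The reasons in XVII.3 for unblinding (preparing the spinal and the block solution, performing sham or active block) separate group 1 from groups 2 and 3 and go no further.

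3. **Patients affected.** At full enrolment, groups 2 and 3 contain 2 × 25 = 50 of 3 × 25 = 75 patients. The plan enrolls 25 per group to retain 23, so its allowance for loss is 25 − 23 = 2 per group, or 2/25 = 8%. The documents do not say how many patients exclusions 11 and 12 are expected to remove.

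4. **The block operator.** XVII.3 calls the operator unblinded, but gives sham versus drug as the reason. XVI has the operator attach the pump in the PACU, where the next action depends on the group. XVII.3 also says that no other research personnel learn the assignment. Read literally, that would leave the operator unaware of the split. No text says when or how the operator learns it.

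5. **Sample size.** For hypothesis 2 the plan uses means of 20 and 49, SD 23 and 15 per group. The difference is 49 − 20 = 29 and the noncentrality is 29 / (23 × √(2/15)) = 3.45 on 28 degrees of freedom. Two-sided power at 0.05 is 91.5%, as stated. Nothing in this calculation depends on how the allocation is disclosed, so staging the disclosure leaves it unchanged.

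**The case against.** The person who certainly knows the split has only a narrow route to the outcome. An investigator places the block and catheters. The anesthetic technique is standardized, the block is a fixed 20 ml per side, and saline under ultrasound confirms every catheter. Narcotic in the spinal does not count toward the primary outcome, intraoperative opioid does not count in the secondary totals, and those who collect data are blinded. This stands as a reason to expect any bias to be limited. It does not answer the route through exclusions 11 and 12, and it gives no reason for disclosing the split early.

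A reader might infer three stronger claims.

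- **That the block operator knows group 2 versus 3 while placing block and catheters.** The documents do not say so, and the XVII.3 sentence confining the assignment to the anesthesiologist points the other way.
- **That catheter positioning in group 2 could be biased in a way that affects opioid use.** Nothing is infused through those catheters, so their position has no such route.
- **That staff who know the group influence rescue.** Patients are "evaluated by the anesthesia pain service for adding a PCA with intravenous hydromorphone if pain not adequately controlled on their regimen", but no text places the anesthesiologist or the block operator in that decision. Withholding the split until the PACU would not address it in any case, since the split must be disclosed there.

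**Conclusion.** The point holds as an avoidable disclosure that is cheap to remove. For the operating-room anesthesiologist it follows directly from the text: the group 2 versus 3 split is known from before the spinal, for 50 of 75 patients at full enrolment, with no operational need until the PACU. For the block operator the documents are unsettled, and sections XVI and XVII.3 must be reconciled.

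It would go too far to say that block and catheter placement are wholly unprotected, or that hypothesis 2 is biased. Neither the size nor the direction of any bias can be derived from the documents, and the safeguards above reduce it without removing it. The conclusion assumes that the envelope is opened before the spinal, as the ITM instruction implies, and that the envelope mentioned at the block step is the same one, since no other is described.

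**What to change.** Replace the single envelope with two sealed, numbered envelopes per patient.

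- **Envelope 1**, opened before the spinal, states only 'ITM + sham block' or 'no ITM + bupivacaine block', with no group number.
- **Envelope 2**, opened in the PACU after both catheters are secured and confirmed, and only by the person attaching the pump, states 'infusion' or 'no infusion'.

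Add to XVII.3 that neither the operating-room anesthesiologist nor the block operator knows group 2 versus 3 before envelope 2 is opened. This also settles the conflict over the operator. Two stages are enough: ITM always goes with the sham block and no ITM with bupivacaine, so a separate card for the block content would conceal nothing.

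The cost is one extra envelope per patient (75 in all) and slightly more preparation by the coordinator. Sample size, treatments and analysis do not change.

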Early oral intake, mobilization, removal of urinary catheter are all important components of the enhanced recovery after surgery protocol (ERAS). We hypothesize that by performing QL blocks post CS the amount of pain, narcotic consumption will be reduced significantly. Early ambulation will help prevent deep vein thrombosis. Performing QL blocks will also minimize side effects secondary to ITM and will facilitate ERAS and better patient satisfaction scores.

A recent study conducted by Salama et al concluded that QLB (without ITM) provided lower numeric rating scores at rest and during movement when compared to the group that received ITM (without QLB). Time to first morphine dose was also longer in the QLB. This study concluded that a longer duration of analgesia and reduced postoperative morphine consumption was achieved with QLB when compared to ITM.(Salama 2019)

X. Sample size

25 in each group

Total number of enrolled patients: 75

XI. Study population

Inclusion criteria

1. Age greater than 18 years
2. Elective C section via Pfannenstiel incision
3. Living singleton pregnancy
4. Gestation week at least 37 weeks
5. ASA status 1, 2 and 3

6. Primary and secondary C sections

Exclusion criteria

1. Chronic pain
2. Opioid tolerant patients
3. Allergy to drugs used in the study.
4. Cognitive dysfunction
5. BMI > 40
6. Coagulation disorder
7. Local infection
8. Inability to tolerate oral medication
9. Previous intra-abdominal surgery
10. Patients who will receive a combined spinal epidural for their C section
11. Local anesthetics injected at any other fascial plane except the QLB plane (for e.g.- local wound infiltration by surgeon)
12. Patients who received sedation or general anesthesia during their CS (midazolam, ketamine, fentanyl, propofol, hydromorphone)

Voluntary patient withdrawal from the study- patient has right to withdraw at any point during the study period

Withdrawal in case of unexpected events- This will be determined by the investigators.

XII. Primary objective

Primary objective of the study is to compare opioid consumption in morphine equivalents between the groups that received postoperative analgesia with intrathecal morphine versus US guided QL blocks versus US guided QL catheters

Our working hypothesis is-

1. Single shot QL block is equivalent to intrathecal morphine with less side effects in providing post-operative pain control for the first 24 hours.

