2. Continuous QL catheter is more beneficial than single shot QL block or intrathecal morphine after 24 hours in providing post-operative pain control.
3. Our exploratory hypothesis is that after 48 hours a QL catheter would continue to reduce morphine consumption until 72 hours.

Primary outcome measure

Total narcotic consumption in morphine equivalents (in milligrams) for the first 72 hours after surgery will be calculated. Total narcotic used in the spinal anesthetic will be excluded.

XIII. Secondary objectives

1. Total narcotic usage at 24 and 48 hours will be assessed in morphine equivalents. Intraoperative consumption of opioids will be excluded.
2. Time to first analgesic request
3. Numeric pain score (NPS)- static and dynamic at 6, 12, 24, 48 and 72 hours
4. Pruritus at 24, 48 and 72 hours
5. Nausea at 24, 48 and 72 hours
6. Vomiting at 24, 48 and 72 hours
7. Sedation at 24, 48 and 72 hours
8. Patient satisfaction- quality of sleep, ability to ambulate, and ability to breast feed and take care of newborn at 24, 48 and 72 hours

Secondary outcome measures-

1. Total narcotic consumption in morphine equivalents (in milligrams) at 12, 24 and 48 hours will be measured.

Time after CS	Total morphine equivalents (mg)
At 4 hours	
At 6 hours	
At 12 hours	

At 24 hours	
At 72 hours	

2. Time to first analgesic request will be reviewed from the chart
3. Our research personnel will use NPS. This will be assessed at 6, 12, 24, 48 and 72 hours. NPS is a 11-point scale as shown below. The study patient will verbally select a numerical value that best corresponds with the pain the patient is experiencing at that point. This data will be statistically analyzed. Static and dynamic pain scores will be assessed. Dynamic pain scores will be assessed by asking the patient to sit up in bed from supine to sitting at 6 hours. This will be repeated at 12, 24, 48 and 72 hours however if patient is ambulating, dynamic pain score during ambulation will be assessed.

No pain

Distressing pain

Worst pain

No pain (0)

Mild pain (1,2,3)

Moderate pain (4,5,6)

Severe pain (7,8,9,10)

Time interval after CS	NPS (static)	NPS (dynamic)
At 6 hours		
At 12 hours		
At 24 hours		
At 48 hours		
At 72 hours		

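### Only group 3 has a running infusion and the plan gives no method for masking a running pump from an idle one, so its blinding claim is unsupported for contrasts with group 3

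*Combined protocol and SAP*

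**What the plan says.** Section XVI describes the trial as double-blinded, with three groups. All three receive bilateral QL catheters. Under Placement of QL catheters, "A member of the research team who performed the initial QLB in the operating room will attach a peripheral nerve pump" once the patient reaches recovery. That sentence is not limited to group 3, so pumps appear to be attached in every arm. Ropivacaine is then started in group 3 at 10 ml/hour on each side. For the others, "We are not initiating any infusion through the peripheral nerve catheters in group 1 and 2"; the reason given is that saline could itself cause pain by distending muscle and fascia.

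The same section adds: "A member of our research team who is blinded to the group allocation will manage all peripheral nerve catheters". The task is not defined, and nobody else is named to look after the pumps after attachment.

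Section XVII.3 says who is unblinded, including the block operator ("Anesthesiologist performing the regional nerve block not be blinded"). It says that other research staff who collect data or see the patient after surgery will not know, among other things, "whether the QLB catheter infusions contain no drug or ropivacaine". Follow-up staff are also called blinded at the end of section XVI and in XVII.5.

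**The concern.** From the recovery unit onward the arms differ in one lasting physical feature: an infusion is running in group 3 and in no other group. Anyone who learns the pump state knows whether the patient is in group 3. The person said to be blinded is assigned to the catheters, and the plan neither keeps the pump out of that role nor says how its state is hidden from that person, the patient or the assessors.

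The outcomes are of a kind that knowledge of treatment can influence. The primary outcome is opioid consumption over 72 hours, and it depends on as-needed dosing: "Oxycodone 2.5 mg-5 mg oral every 4 hours as needed will be added for breakthrough pain". The pain service may add PCA hydromorphone if control is inadequate. Pain, side-effect and satisfaction scores are self-reported. The exposed hypotheses include the second, "Continuous QL catheter is more beneficial than single shot QL block or intrathecal morphine after 24 hours", which is one of the two that the trial is sized to confirm.

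**Working it through.** **Statements side by side**

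| Feature | Group 1 | Group 2 | Group 3 | Source |
|---|---|---|---|---|
| Catheters on both sides | yes | yes | yes | XVI |
| Pump attached (sentence not limited by group) | apparently | apparently | yes | XVI, Placement of QL catheters |
| Infusion started | no | no | yes | XVI, Placement of QL catheters |
| Method for masking pump state | none described | none described | none described | whole document |

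**What each safeguard covers**

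- Opaque envelopes and separate allocating staff protect the assignment.
- The sham block addresses the single-shot injection.
- Catheters, and apparently pumps, in every arm mean that having the equipment does not reveal the group.
- Omitting dermatome testing removes a clinical cue. The plan's stated reason is that testing could reveal the group to patients and staff.
- XVII.3 states that infusion content will be unknown to postoperative research staff. This is a commitment without a procedure.

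None of these is described as hiding pump state. The document does not mention a covered display, a masked reservoir or a separate unblinded pump handler.

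**How long the difference lasts**

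The group 3 rate is 10 ml/hour × 2 sides = 20 ml/hour. That is 20 × 24 = 480 ml by 24 hours and 20 × 48 = 960 ml by 48 hours. It would be 20 × 72 = 1440 ml by 72 hours if the infusion ran that long, but no stop time is given. Groups 1 and 2 receive 0 ml by this route.

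**How much of the trial is exposed**

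- Patients (section X: 25 per group, "Total number of enrolled patients: 75"): 25/75 = 33% with a running infusion and 50/75 = 67% with none. At the pre-inflation size of 23 per group (XIX) the proportions are the same: 23/69 and 46/69.
- Pairwise contrasts: 3 versus 1 and 3 versus 2 are exposed, and 1 versus 2 is not. That is 2 of 3.
- Hypotheses (XII): the second and third concern the catheter arm and are exposed. The first compares groups 1 and 2, neither of which has an infusion, and is not. That is 2 of 3.

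**The plan's own figure for the exposed contrast**

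For hypothesis 2, section XIX uses means of 20 and 49, SD 23, 15 per group and a two-sided 0.05 t test, and states 91.5% power. The noncentrality is 29 / (23 × √(2/15)) = 29 / 8.40 = 3.45 on 28 degrees of freedom, which gives 91.5%. The figure reproduces, and at 23 per group the power is 98.7%. Neither value depends on blinding, so this point leaves the sample size as it is.

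**The case against.** There is a fair case on the other side, and several parts of it stand.

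- A reader might infer that XVII.3 contradicts XVI, because it speaks of what infusions contain when two arms have no infusion. The documents do not support that. The plan uses no drug to mean that nothing is given: the sham is an empty syringe, and group 1 is said to receive no drug. Read in the same way, XVII.3 covers idle versus running pumps. What is missing is a method; the two sections do not conflict.
- A reader might infer that the existing safeguards are shown to fail. They are not. The text names a pump model but says nothing about its display, sound or reservoir, or about whether idle pumps are powered or covered. The plan is silent on masking, and silence does not prove unblinding.
- A reader might infer that ward staff and the pain service are claimed to be blinded. No section says so; the explicit statements concern research personnel. Patient blinding is implied by the double-blind label and by the reason given for omitting dermatome testing.
- Managing catheters could mean only site care, dressings and removal. That reading is possible, because the task is undefined. It would leave pump care unassigned, and it would not say how pump state is hidden from patients or assessors.
- Leaving out saline was a reasoned choice, and nothing here asks for it to be reversed.

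These points limit the strength of the criticism. They do not supply the missing method.

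**Conclusion.** The point holds as a gap in support for a claim. As written, the double-blind description and the blinded-staff statements are not supported for contrasts with group 3, and so for hypotheses 2 and 3 and for the catheter comparisons in the 72-hour primary outcome. This is more than missing detail, because the outcomes are as-needed opioid use and self-report, and because the blinded catheter role may bring its holder into contact with the one feature that identifies group 3.

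The counts above show how many contrasts are exposed. They do not measure harm, and the documents allow neither the size nor the direction of any bias to be derived. The conclusion assumes that pumps are attached in all arms, which is the reading most favourable to the plan. If they were attached only in group 3, the presence of a pump would itself identify the group.

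The stronger conclusion, that blinding will fail in practice, is not available from these documents. The plan should be amended, but the design can stand.

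**What to change.** 1. **Section XVI, Placement of QL catheters.** Give pump handling to the block-team member, who is already unblinded under XVII.3. State that this person collects no outcome data and takes no part in rating outcomes. Define any blinded catheter role so that it is limited to tasks that do not expose pump state.
2. **Masking.** Mask the pump display and reservoir in the same way in all three arms, with access for safety checks, and have outcome assessors stay away from the pumps. No saline infusion is needed.
3. **Sections XVI, XVII.3 and XVII.5.** State who is blinded to what, naming at least patients, assessors and the catheter manager. Where pump state cannot be masked, do not describe contrasts with group 3 as double-blind.

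The cost is a protocol amendment, simple covers and a change of role within the existing team, with no added patients or staff. The downsides are more work for the block team, postoperative patient contact by an unblinded team member, possible residual cues such as noise or reservoir changes, and a more modest blinding claim.
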